7.2 SECONDARY EFFICACY ANALYSES

7.2.1 Cumulative incidence of the composite primary endpoint

Endpoint

Cumulative incidence of the composite primary endpoint. All the observed events for each patient over the total duration of follow-up will be considered. Patients with multiple events on a given day will be considered as having one event on that day. For virological events only first episode was considered and data were censored at the time of treatment discontinuation.

Descriptive statistics and graphical representation

The cumulative incidence of the primary composite endpoint will be summarized with the total number of events, person-years, and the incidence rates per 100 person-years by treatment group (Integrase inhibitor versus Protease inhibitor).

Statistical methodology

In this analysis, the event is the sum of all episodes of the composite primary endpoint. For this analysis, the entire follow-up will be considered (i.e. follow-up will begin at baseline and continue until the 48-week visit, study discontinuation, loss to follow-up; whichever occurs first). All participants will be censored on the date of their last observation.

The cumulative incidence of the composite primary endpoint will be estimated by the total number of events divided by the total number of person-years of observation. The person-year is the total sum of the number of years that each subject of the study population has been under observation. The number of years each subject would have been under observation will be calculated by the difference between the date of the last observation and the date of study treatment initiation plus one, divided by 365.25.

The effect of study treatment will be assessed using a Poisson regression model adjusted for the stratification factor (country/group of neighbouring countries and baseline CD4 cell counts (<50 or $\geq50/\mu\text{L}$)). An adjusted incidence rate ratio (IRR) and the associated 95% CI will be calculated.

All P-values will be two-tailed with a significant level at 5%.

This analysis will only be performed if it is added additional information: i.e. if the number of cumulative episodes is greater than that of the first episode (with at least 10 additional events).

7.2.2 HIV-RNA viral load <50 copies/mL at week 24, 36 and 48

Endpoint

The proportion of patients with HIV-RNA viral load <50 copies/mL at week 24, 36 and 48 using the snapshot approach.

Virologic outcome will be determined by the last available measurement while the participant is on treatment and continues on trial within the time window. The time window for each timepoint is defined in Table A below.

Table A: Proposed Windows

Visit	Window (Through End-of-Study Week)	Window (Days)
24	18-30	127-210
36	30-42	211-294
48	42-54	295-378

Descriptive statistics and graphical representation

The analyses will be performed with the mITT population and DPS1. Data will be summarized with the number and percentage of participants with an event.

The proportion of patients with HIV-RNA viral load <50 copies/mL, HIV RNA viral load \geq 50 copies/mL, discontinuation due to Adverse Event (AE/SAE), discontinuation due to other reasons or on study but missing data at analysis time point will be calculated. The evolution over time will be analysed graphically using trend analysis.

HIV-RNA \geq 50 copies/mL includes: patients who changed any component of background therapy to a new drug class, changed background components that were not permitted per protocol, or changed any background drug in the regimen because of lack of efficacy (perceived or documented) before Week 48; patients who discontinued study drug or study before Week 48 for lack or loss of efficacy and patients who are equal to or above 50 copies/mL in the 48-week window.

AE/SAE includes: patients who discontinued because of adverse event (AE) or death at any time point from baseline through the time window if this resulted in no virologic data during the specified window.

Other Reasons includes: withdrew consent, loss to follow-up, moved, among others.

Statistical methodology

The proportion of patients with HIV-RNA viral load <50 copies/ml, HIV-RNA viral load \geq 50 copies/ml, discontinuation due to adverse event (AE/SAE), discontinuation due to other reasons or participating in the study but with missing data at the time of analysis will be calculated by dividing the number of participants with an event of interest by the total number of participants in the mITT population.

The effect of study treatment on the proportion of patients with HIV-RNA viral load <50 copies/ml at week 24, 36 and 48 will be assessed using a logistic regression model with treatment group and adjustments for stratification factor (country/group of neighbouring countries and baseline CD4 cell counts (<50 or \geq 50/ μ L)). An adjusted odds ratio (OR) and the associated 95% Confidence Interval (CI) will be calculated.

In addition, we will use Cochran-Mantel-Haenszel tests to assess the difference between treatments in the percentage of participants with HIV-RNA viral load <50 copies/ml at week 48 (ie, response rate in BIC group minus the response rate DRV/c group) adjusted for country/group of neighbouring countries and baseline CD4 cell counts (<50 or \geq 50/ μ L). All P-values will be two-tailed with a significant level at 5%.

7.2.3 Genotypic resistance test among patients with virological failure

Endpoint

Number and percentage of patients with drugs resistance mutations among patients with virological failure. Drugs resistance mutations will be identified from the Stanford drugs resistance interpretation algorithm (last version at the time of analysis).

<https://hivdb.stanford.edu/dr-summary/mut-scores/NRTI/>
<https://hivdb.stanford.edu/dr-summary/mut-scores/NNRTI/>
<https://hivdb.stanford.edu/dr-summary/mut-scores/PI/>
<https://hivdb.stanford.edu/dr-summary/mut-scores/INSTI/>.

Descriptive statistics and graphical representation

The analyses will be performed on patients with virological failure in the mITT population for whom genotypic sequences have been obtained. Data will be summarized with the number and percentage of participants with drugs resistance mutations.

Statistical methodology

The proportion of participants with drugs resistance mutations will be calculated by dividing the number of participants with drug resistance mutations by the total number of participants with virological failure for whom genotypic sequences have been obtained. The frequency of each resistance mutation will be indicated.

Fisher's exact test will be used to compare the presence of at least one drug resistance mutation between the 2 groups.

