9.3.3 Secondary outcome analysis

All secondary outcome analysis will be done with the ITT population. The p-values will be two-tailed, with a significant level of 0.05.

The proportion of patients with HIV-ribonucleic acid (RNA) viral load <50 copies/mL at week 48 will be analysed using the snapshot approach. Fisher's exact test will be used to compare the estimated proportion between the two groups.

A genotypic resistance test will be performed in all patients with virological failure. Drugs resistance mutations will be identified from the International AIDS Society (IAS)-USA resistance testing panel (last version at the time of analysis) and for BIC we will use IAS, Agence Nationale de Recherches sur le SIDA (National Agency for AIDS Research) (ANRS) or Royal College of Physicians (RCP) lists to perform the analysis whenever they will be made available. Resistance to BIC will also be identified using phenotypic resistance test. Fisher's exact test will be used to compare the presence of at least one drug resistance mutation between the 2 groups.

The median time to reach CD4 cell count >200/ μ l will be estimated using the Kaplan-Meier method, censoring at week 48 or last follow-up date if not seen at week 48. Time to reach CD4 cell count >200/ μ l will be defined as the time between the date of study treatment initiation (baseline, week 0) and the date of which patient reached CD4>200/ μ l. The log-rank test will be used to compare the two survival functions. The p-values will be two-tailed, with a significant level of 0.05. The proportion of patients with CD4 cell count <350/ μ l at week 48 will be done with the ITT population, with the last observation carried forward (LOCF) approach. Fisher's exact test will be used to compare the 2 groups.

The median change in CD4/CD8 ratio from baseline to week 48 will be analysed with the ITT population, with the LOCF approach. The non-parametric Mann Whitney test will be used to compare the change from baseline between the 2 groups.

The incidence of IRIS will be analysed with the Kaplan-Meier method. The Log-rank test will be used to compare the two survival functions. The effect of study treatment on IRIS will be assessed using Cox regression model with treatment group and adjustments for stratification factors.

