3	Eligibility	According to the inclusion/exclusion criteria.
4	Medical & social history	
Including:
 
 • Recreational drug use • Smoking history • Alcohol intake • Concomitant diseases • Past & present medical history, including HIV- associated conditions • Review of any medication taken within the last 30 days
5	ECG	12-Lead ECG performed supine. If an ECG is not performed at screening, it must be performed by the time of the baseline visit.
6	HBV & HCV testing	
HBV antigen test and hepatitis C (HCV) antibodies test (if patient tests positive for HCV antibodies, test for HCV RNA, if positive and chronic for either HBV or HCV, add HBV DNA test at baseline visit).
 
HBV test to be repeated in event of positive result. Participants with active HBV infection at study entry will be monitored throughout the study and additional HBV DNA tests performed at the Week 24 and 48 visits.
 
For screening, test results 28 days prior to the screening visit can be used

7	Latent TB Testing	
A Latent TB test (IGRAs e.g. ELISPOT, QuantiFERON) may be performed in patients with expected latent TB at the screening visit. For screening, test results 28 days prior to the screening visit can be used.
 
Patients can be randomised into the study without having the latent TB screening results available at randomisation
 
A TB test can be performed at subsequent visits because of clinical suspicion.

	Assessment sub notes	Parameters/Notes
8	Resistance testing (performed locally)	
A local resistance test will be performed at the screening visit. This result is not required for eligibility or prior to randomisation. If a HIV resistance test was done previously and results are available, the last resistance test carried out shall be considered.
 
An additional resistance test will be performed at the ETV for patients with virological failure or insufficient virological response.

9	Vital Signs (10 mins resting)	
Including:
 
 • Pulse • Blood pressure

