2.1.2 Secondary objectives

The secondary objective of this study is to investigate the immunological and virologic response, tolerability, resistance development, discontinuation of therapy due to tolerability, quality of life (QoL) and IRIS incidence.

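### The resistance comparison in SAP 7.2.3 counts any listed mutation present at failure, so it does not measure the stated objective of resistance development

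*Combined protocol and SAP*

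**What the plan says.** The endpoint in SAP 7.2.3 is "Number and percentage of patients with drugs resistance mutations among patients with virological failure". Four Stanford pages define the mutations (NRTI, NNRTI, PI and INSTI); the NNRTI page is cited as "https://hivdb.stanford.edu/dr-summary/mut-scores/NNRTI". The count is divided "by the total number of participants with virological failure for whom genotypic sequences have been obtained". For the comparison, "Fisher's exact test will be used to compare the presence of at least one drug resistance mutation between the 2 groups". SAP Table 8 carries the same percentage. Protocol v5.0, 9.3.3, plans the same any-mutation test, with a different source list, and sets the level for secondary outcomes: "The p-values will be two-tailed, with a significant level of 0.05".

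The objective in SAP 2.1.2 is to "investigate the immunological and virologic response, tolerability, resistance development", among other items. The endpoint listed in SAP 2.2.2 is worded as drug resistance at confirmed failure.

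On baseline data, protocol v5.0, Appendix 1, note 8, says: "A local resistance test will be performed at the screening visit". The same note says that the result is not needed before randomisation and that an earlier test may be used. SAP 6.3.2 and Table 1B summarise baseline mutations by arm on the Stanford lists. Baseline and on-treatment samples are stored for central deep sequencing.

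**The concern.** A patient counts as positive under 7.2.3 whether the mutation was selected during the trial or was there before the first dose. The two have different meanings. Only the first bears on whether one regimen generates more resistance than the other, which is what the objective asks. The plan recognises the distinction elsewhere: the last secondary endpoint in SAP 2.2.2 names baseline mutations and mutation development as separate reasons for changing drug. Section 7.2.3 merges them.

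If this is the only tested resistance result, readers will take it as the answer on resistance development. Mutations that predate treatment would raise the percentage in both arms and could obscure a real difference in emergence.

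**Working it through.** **Step 1. Does 7.2.3 require a mutation to be new?** No. It sets no condition of absence at baseline, no restriction to the classes of drug given, and no link to the genotypes behind Table 1B.

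**Step 2. Can pre-existing mutations be present?** Yes, by three routes.
- The screening genotype need not be available before randomisation (protocol v5.0, Appendix 1, note 8; SAP 3.3, note 8).
- Under protocol 6.1.3, the listed resistance patterns prevent randomisation only if the result arrives in time. If an FTC/tenofovir pattern (Table 2 there) is reported later, the patient may stay in the assigned arm.
- Exclusion criterion 4 covers known resistance to components of the study drugs. No criterion excludes NNRTI mutations, and neither randomised regimen (BIC/FTC/TAF or DRV/c/FTC/TAF) contains an NNRTI.

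**Step 3. Does another analysis measure emergence?** No. SAP 10.1.4 counts patients whose study drug was stopped or changed. SAP 10.2.1 compares two sequencing methods. Table 1B gives arm totals over all patients and cannot show which patient's mutation at failure is new.

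**Step 4. Illustration of size.** The plan states no rate, sample size or power for this endpoint, so there is no figure to reproduce.

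Inputs from the documents: 220 patients per arm and 20% virological failure at week 48 in the darunavir reference group (SAP 4), giving 0.20 × 220 = 44 failures; two-sided level 0.05.

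Assumptions, not in the documents: 44 sequenced failures in each arm; emergent resistance e of 0% (INI) and 15% (PI) among failures; baseline carriage b of 0 to 20%, equal in the arms and independent of emergence.

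The proportion counted under 7.2.3 is 1 − (1 − b)(1 − e). For the PI arm at b = 10%: 1 − 0.90 × 0.85 = 0.235. Power is exact, from enumerating the two binomial distributions. Emergent cases number 44 × 0.15 = 6.6 throughout.

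| b | Counted, INI v PI | Patients counted | Without an emergent mutation | Fisher power |
|---|---|---|---|---|
| 0% (emergent only) | 0.0% v 15.0% | 6.6 | 0 | 0.66 |
| 5% | 5.0% v 19.3% | 10.7 | 4.1 (38%) | 0.43 |
| 10% | 10.0% v 23.5% | 14.7 | 8.1 (55%) | 0.29 |
| 20% | 20.0% v 32.0% | 22.9 | 16.3 (71%) | 0.17 |

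**Step 5. Sensitivity.** Emergent rates of 0 v 10%, 0 v 15% and 2 v 20% were tried with 44 v 44 and with 22 v 44 failures (INI v PI). At 5 to 20% carriage, 23% to 79% of counted patients have no emergent mutation. Power falls with carriage in every set but one. With 22 v 44 failures and 0 v 10% emergence it is 0.07 without carriage and 0.08 to 0.12 with it, so there is almost no power under either definition.

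**The case against.** The strongest reply is that 7.2.3 does what was listed. The secondary endpoint describes resistance at failure, and protocol 9.3.3 plans a test of the presence of at least one mutation. A reader might infer that the SAP departs from the protocol here; it does not. The mismatch is with the objective, so the proportionate request is an added analysis, with the listed endpoint kept.

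The plan also gives partial help. The frequency of each mutation will be shown, so NNRTI mutations will be visible, and Table 1B shows baseline mutations by class and arm. This softens any claim that the data would be hidden, but it does not identify emergence patient by patient.

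Three further inferences go beyond the documents.
- That every patient has a usable baseline genotype: an older test may be used, and Table 1B has a No/Yes row for resistance testing.
- That pre-existing mutations add the same background to both arms: failures are a subset formed after randomisation, so carriage among them may differ by arm. Bias is then possible as well as dilution.
- That study patients could not acquire NNRTI mutations on treatment: switches to other regimens are allowed, and their content is not fixed. What can be said is that neither randomised regimen contains an NNRTI.

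It is also fair to say that the subset is small, so power for emergent resistance is modest even without contamination (0.66 in the main illustration).

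**Conclusion.** The point holds in a limited form. The count in 7.2.3 is a legitimate measure of resistance present at failure, but it does not measure resistance development, and nothing else in the SAP does. Inflation of the percentages follows for any carriage above zero. Dilution of a between-arm difference is likely and bias is possible.

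The size cannot be derived from the documents, which give neither baseline carriage nor emergence rates. The fall in power from 0.66 to 0.17 rests wholly on the assumptions in step 4. A reader might infer that the plan would turn a significant resistance difference into a non-significant one; that depends on the rates chosen, and the documents do not support it as a prediction.

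Severity is low: this is a secondary endpoint in a small subset, and the primary conclusion is unaffected. It is worth changing because the change is cheap.

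**What to change.** In SAP 7.2.3 and Table 8:
- Add treatment-emergent resistance as the between-arm comparison for the resistance-development objective. Define it as at least one NRTI, PI or INSTI mutation in the failure genotype that is absent from the same patient's screening or baseline genotype.
- Compare like with like: local with local, or central deep sequencing of both samples at a common threshold. Filling a missing local baseline result from deep sequencing would make emergence depend on the assay, and SAP 10.2.1 itself asks whether the methods differ. If the central route is chosen, settle whether that sequencing is optional (protocol 6.6.1) or definite for failures (Appendix 1, note 14).
- Classify failures without a usable baseline sequence as emergence not assessable, and report their number by arm.
- Keep the protocol-listed any-mutation count as descriptive, showing mutations present at baseline and NNRTI mutations separately.

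The cost is SAP wording and a merge of genotype data that the trial already collects. Fewer cases will be counted and some failures will not be assessable. SAP 5.1 allows the SAP to be updated before sign-off.

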7.2.4 Time to reach CD4 cell count >200/ μ L

Endpoint

The median time to reach CD4 cell count >200/ μ L.

Descriptive statistics and graphical representation

The analyses will be performed with the mITT population with CD4≤200/ μ L at baseline and DPS1. Data will be summarized with the number and percentage of participants achieving a CD4 cell count >200/ μ L and the median (95% CI) time to reach a CD4 cell count >200/ μ L. Kaplan-Meier curves will also be plotted.

Statistical methodology

Kaplan-Meier method will be used to estimate the proportion of participants achieving a CD4 cell count >200/ μ L and the median time to achieve a CD4 cell count >200/ μ L. The follow-up will begin at baseline (date of study treatment initiation) and continue until the week 48 visit, study discontinuation, loss to follow-up, or onset of a CD4 cell count >200/ μ L; whichever occurs first. Participants lost to follow-up or who have discontinued the study with a CD4≤ 200/ μ L will be censored at the date of last observation.

The effect of study treatment on the time to reach a CD4 >200/ μ L will be assessed using Cox regression model with adjustments for stratification factor (country/group of neighbouring countries and baseline CD4 cell counts (<50 or ≥50/ μ L)). An adjusted HR and the associated 95% CI will be calculated. All P-values will be two-tailed with a significant level at 5%.

7.2.5 CD4 cell count <200/ μ L and <350 at week 4, 8, 12, 24, 36 and 48

Endpoints

- The proportion of patients with CD4 cell count <200/ μ L at week 4, 8, 12, 24, 36 and 48
- The proportion of patients with CD4 cell count <350/ μ L at week 4, 8, 12, 24, 36 and 48

Descriptive statistics and graphical representation

The analyses will be performed with the mITT population and DPS1. Data will be summarized with the number and percentage of participants CD4 cell count <200/ μ L and <350/ μ L. The evolution over time will be analysed graphically using trend analysis.

Statistical methodology

The evolution of the proportion of participants with CD4<200/ μ L and <350/ μ L over time will be compared between the 2 treatment groups (DRV/c versus BIC) using a Generalized Estimating Equation (GEE) models with independent covariance structure, binomial distribution and log link, to estimate the relative risk. The models will include treatment group, time, and interaction between treatment group and time. Time will be modelled as categorical variable. A relative risk (RR) and the associated 95% CI will be calculated. All P-values will be two-tailed with a significant level at 5%.

7.2.6 Change in CD4/CD8 ratio from baseline to week 48

Endpoints

The change in CD4/CD8 ratio from baseline to week 48.

Descriptive statistics and graphical representation

The analyses will be performed with the mITT population and DPS1. Data will be summarized in tables by mean and standard error. The evolution of CD4/CD8 ratio will be described by boxplots for each treatment group at each time point. The number of participants with data available at each time point will also be reported.

Statistical methodology

The mean change in CD4/CD8 ratio from baseline to week 48 will be compared between the 2 treatment groups using a mixed model with random intercept and slope and spatial power covariance structure due to unequal time intervals between visits. The models included treatment group, time, and interaction between treatment group and time. Time was modelled as a categorical variable. All P-values will be two-tailed with a significant level at 5%.

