3.2 RANDOMISATION SCHEME AND BLINDING

The randomization list will be generated by an independent statistician not part of the study team. The list will be generated by a centralized computer-generated random list with a permuted block size. He is the only person who know the size of the blocks.

Participants will be randomly assigned, in a 1:1 ratio, to receive a BIC containing regimen or boosted PI containing regimen for 48 weeks, with allocation stratified by country and baseline CD4 cell count (<50 cells/µL, 50-199 cells/µL, or ≥200 cells/µL).

Randomization will be done at the baseline visit (date of the study treatment initiation). This study is open-label; therefore, all investigators, site pharmacists, study nurses and participants will be unmasked and aware of the treatment allocation throughout the study.

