6.5 STRATIFICATION FACTOR

The stratification variable is consisted of two variables: participating country (7 countries: UK, Spain, France, Belgium, Germany, Ireland, and Italy) and baseline CD4 cell count (<50, 50-199, ≥200). Overall, 21 strata will be considered. Based on the large number of strata, we anticipated some few participants in some strata. In country that will recruit fewer than 10 participants, we will group together some neighboring countries. In addition, with regard to CD4 cell count, we will group together participants whose value is between 50-199 and ≥200/µl to obtain 2 categories (<50 versus ≥50/µl) because of the anticipated small number of participants in the latter category. These new variables will be used for adjustments.

The number and proportion of participants in each stratum will be reported by treatment group and overall. The exact list of strata will also be presented.

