The follow-up will begin at baseline and continue until the week 48 visit, study discontinuation, loss to follow-up, or onset of the composite primary endpoint events; whichever occurs first. Participants lost to follow-up or who have discontinued the study when they are endpoint free at time of leaving the study will be censored at the date of last observation.

The effect of study treatment will be assessed using Cox regression model with treatment group and adjustments for stratification factor (country/group of neighbouring countries and baseline CD4 cell

counts ($<50/\mu\text{L}$ or $\geq50/\mu\text{L}$), as the sample size would not allow use of the stratification factors of randomisation (country and baseline CD4 in three categories (<50 ; $50-199$; $\geq200/\mu\text{L}$)). An adjusted hazard ratio (HR) and the associated 95% Confidence Interval (CI) will be calculated. Separate analyses for each component of the primary endpoint will be done. All P-values will be two-tailed with a significant level at 5%.

A sensitive analysis will be performed with the per-protocol population and DPS2.

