9. SUBGROUP ANALYSES

Subgroup analyses for the composite primary endpoints will be performed to assess the consistency of the effect of study treatment across the subgroups. The analysis will be performed with the mITT population. The following baseline variables will be studied (continuous variables will be categorized into terciles):

- age at inclusion (categorized into terciles)
- country
- group of neighbouring countries
- baseline CD4 cell counts (<50 or 50-199 or \geq 200/ μ L)
- baseline CD4 cell counts (<50 or \geq 50/ μ L)
- gender
- transmission group
- ethnic group
- baseline viral load (<100,000, 100,000-500,000, $>$ 500,000)
- Current smoker (no or yes)
- adherence (take medication all the time versus not at all)

If the number of participants is too small (less than 10) within a subgroup, then the subgroup categories may be redefined before locking the database. A forest plot will display confidence intervals across subgroups.

We will use a Cox proportional hazard model to calculate the hazard ratio between BIC and DRV/c of the incidence of the first episode of the composite primary endpoint event in each subpopulation, without adjustments for stratification factors. The heterogeneity of the effect of BIC and DRV/c within subgroups will be assessed by including terms for interactions between treatment group and subgroup variables in a Cox proportional hazard model.

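### The GEE for CD4 below 200 and below 350 (SAP 7.2.5) leaves out the stratification factors, so its intervals are somewhat conservative; adding them needs a baseline CD4 by time term and a Poisson fit

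*Combined protocol and SAP*

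**What the plan says.** Randomisation is 1:1, "with allocation stratified by country and baseline CD4 cell count" (SAP 3.2). SAP 6.5 groups countries that recruit few participants, reduces baseline CD4 to <50 versus ≥50, and concludes: "These new variables will be used for adjustments".

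The GEE in SAP 7.2.5 is specified "with independent covariance structure, binomial distribution and log link, to estimate the relative risk", and its terms are given in full: "The models will include treatment group, time, and interaction between treatment group and time". SAP Table 5 shows that week 0 is one of the visits and that the reported contrasts run from baseline to each later week.

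SAP 7.2.6 analyses the CD4/CD8 ratio "using a mixed model with random intercept and slope and spatial power covariance structure due to unequal time intervals between visits". Again, "The models included treatment group, time, and interaction between treatment group and time", with nothing else listed.

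Neither section gives a reason for leaving the factors out. The adjusted analyses include time to CD4 above 200 (7.2.4), the snapshot response, IRIS, hospitalisation and safety. The same kind of mixed model is adjusted for the health status and symptom scores (10.1.3) and for laboratory parameters (10.1.6).

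**The concern.** Baseline CD4 is the natural predictor of later CD4, and it was a randomisation stratum. Of all the secondary endpoints, the CD4 endpoints are where one would most expect it in the model. Stratified allocation makes the arms nearly equal on baseline CD4, so the treatment estimate already varies less than under simple randomisation. A model without the stratum does not know this: its standard error still counts the between-stratum variation. A robust variance does not help, because it too treats patients as if they had been allocated without strata.

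At stake is precision on immunological response, which is named in the secondary objective, and consistency between neighbouring analyses of the same measurement.

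**Working it through.** **The plan's own figures.** SAP section 4 sizes only the primary endpoint, and this point does not touch it. The margin is ln 0.63 / ln 0.75 = 1.606. Events are (1.960 + 0.842)² / [0.25 × (ln(1.606/0.909))²] = 96.9, so 97, and 97 / 0.24 = 404 evaluable. No precision or power is stated for 7.2.5 or 7.2.6.

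**Size of the effect at week 48, CD4 below 200.** The documents give no stratum shares, stratum risks or block size, so these are assumptions: shares of 50/45/5% for <50, 50–199 and ≥200; blocks of 4; three sets of risks. With the collapsed split (<50 versus ≥50, each half of the patients), the unadjusted-to-adjusted SE ratio is roughly 1/√(1 − B/T), where

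- T = p(1 − p), with p the overall risk;
- B = 0.25 × (risk in <50 − risk in ≥50)²;
- risk in ≥50 = 0.9 × (risk in 50–199) + 0.1 × (risk in ≥200).

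| Assumed risks by stratum | Risk in ≥50 | p | T | B | SE ratio |
|---|---|---|---|---|---|
| 45/40/10% (weak) | 0.370 | 0.410 | 0.2419 | 0.0016 | 1.003 |
| 60/35/10% (moderate) | 0.325 | 0.4625 | 0.2486 | 0.0189 | 1.040 |
| 70/25/5% (strong) | 0.230 | 0.465 | 0.2488 | 0.0552 | 1.134 |

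A simulation of 3,000 trials of 440 patients per scenario compared the unadjusted relative risk with a Mantel-Haenszel relative risk stratified by country and collapsed CD4. This stands in for the GEE at week 48.

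| Scenario | SE ratio (no effect) | Coverage, unadjusted / adjusted | Type I error | Power at RR 0.8 |
|---|---|---|---|---|
| Weak | 1.003 | 95.0 / 95.1% | 5.0 / 4.9% | 42.7 / 42.8% |
| Moderate | 1.040 | 96.4 / 95.7% | 3.6 / 4.3% | 50.7 / 53.3% |
| Strong | 1.134 | 97.0 / 95.0% | 3.0 / 5.0% | 50.9 / 59.2% |

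In the strong case the two estimates really vary by the same amount (empirical SD 0.093 and 0.092), but the unadjusted model reports a mean SE of 0.103 against 0.091. The excess is in the reported SE, not in the estimate.

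**Which adjustment works.** A log-link model with a CD4 main effect imposes one risk ratio r between the CD4 groups at every visit. At week 0 everyone in the <50 and 50–199 strata is below 200 by definition, so the overall risk is about 0.95. A Poisson fit with all arm-by-visit terms reproduces that mean. If the ≥50 group has fitted risk x, then 0.5rx + 0.5x = 0.95, and the <50 group is fitted at rx = 1.9r/(1 + r). This exceeds 1 once r exceeds 1/0.9 = 1.11. The week-48 ratios assumed above are 0.45/0.37 = 1.22, 0.60/0.325 = 1.85 and 0.70/0.23 = 3.04.

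A GEE simulation with 440 patients, seven visits and assumed shares of 52/43/5% bears this out:

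- With the CD4 main effect, the largest fitted risk averaged 1.26, and there was no valid log-binomial fit in 40 of 40 trials. The SAP's model failed in none of 40.
- SE of the arm by week-48-versus-week-0 contrast: 0.1186 without adjustment, 0.1186 with the main effect, 0.1069 with CD4 by time.
- SE of the week-48 relative risk alone: 0.1207 without adjustment, 0.1093 with the main effect.

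Under another set of assumed inputs, Poisson with CD4 by time lowered both SEs by about 4 to 5%.

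**CD4/CD8 (7.2.6).** A mixed model with random intercept and slope (assumed variances, no spatial-power residual) gave an SE for the arm by week-48 contrast of 0.00979 both without and with main effects for country and CD4. CD4 by time gave 0.00956. With 10% of visits missing the three values were 0.00989, 0.00989 and 0.00960.

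**The case against.** The strongest reply is that nothing is invalidated. The error is conservative, its size rests on assumed risks, and with a weakly prognostic baseline CD4 it disappears. The protocol's own week-48 tests for CD4 below 350 and for CD4/CD8 (Fisher, Mann-Whitney) were also unadjusted, and immunological recovery already has an adjusted analysis in 7.2.4. Nor are these the only unadjusted comparisons: resistance uses Fisher's test, the EQ-5D dimensions a chi-square test, and the GEE for binary urine parameters lists no covariates. The obvious adjustment, a CD4 main effect in the log-binomial model, would break the fit. All of this stands. It limits the point to precision and consistency, and it decides the form of the fix.

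Three stronger readings are tempting but not supported.

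- A reader might infer that the subgroup hazard ratios, computed "in each subpopulation, without adjustments for stratification factors", also have intervals that are too wide. Simulated Cox models with stratum hazard ratios of 1.5 to 3 had equal mean SEs with and without the stratum (0.192 with no effect, 0.176 at a hazard ratio of 1.606) and 94–96% coverage either way. The only effect is slight attenuation, from 1.606 to about 1.56 at most. The omission is an explicit choice, and SAP 5.5 labels these analyses exploratory.
- A reader might infer that the primary model loses by collapsing the factors, "as the sample size would not allow use of the stratification factors of randomisation". That reason is open to question for main effects: seven countries and three CD4 levels need 6 + 2 = 8 parameters against 97 events. But full and collapsed factors gave the same simulated SE (0.1936), and SAP 6.5 sets out the CD4 collapse and the trigger for grouping countries in advance. There is no precision case for undoing it.
- A reader might infer that the CD4/CD8 intervals are too wide. The random intercept already absorbs factors that are constant over time, so main effects leave the change contrast as it was.

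**Conclusion.** The omission in 7.2.5 is real, unexplained and at odds with SAP 6.5 and 7.2.4. Its consequence is a reported standard error about 0 to 13% too large for the week-48 relative risk of CD4 below 200. Coverage is 95.0 to 97.0%, type I error is at or below nominal, and up to about 8 points of power are lost at a relative risk of 0.8. These figures rest on assumed stratum shares, stratum risks and block size, and on a Mantel-Haenszel stand-in for the GEE; CD4 below 350 was not calculated separately. In 7.2.6 the omission is an inconsistency with 10.1.3 and 10.1.6, with no precision at stake from main effects. The primary analysis is adjusted and unaffected. This is a modest improvement worth making, not a threat to validity.

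**What to change.** In SAP 7.2.5, add country group, baseline CD4 (<50 or ≥50) and a baseline CD4 by time interaction, and fit the GEE as a log-link Poisson model with robust variance in place of the log-binomial. State how convergence problems will be handled. In SAP 7.2.6, list the same covariates so that the model matches 10.1.3 and 10.1.6.

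The cost is SAP wording, the convergence rule and a few parameters. With seven visits these are 1 for CD4, 6 for CD4 by time and at most 6 for seven countries, on top of the 14 arm-by-visit terms. The covariates are already derived under 6.5. No change is needed to the factors in 7.1 or, on grounds of interval width, to section 9.
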